7.1 Timing of Analyses

The final analysis will be performed after the last patient has completed the last (6-month) follow-up visit, and all data have been transferred to a separate file on having been documented as meeting the cleaning and approval requirements of the primary investigator and after the finalisation and approval of this Statistical Analysis Plan. Only when these requirements have been met, will database lock occur, and the randomisation code be opened.

7.2 Analysis Populations

7.2.1 Intention-to-treat Population (Primary analyses)

All subjects who were randomised. For the primary endpoint, only patients who (irrespective of receipt of actual treatment) performed an adequate cardiopulmonary exercise test at baseline and follow-up can be analysed. The adequacy of the cardiopulmonary exercise test must be determined before database lock and the randomisation code is opened.

7.2.2 Per Protocol Population

All subjects actually received the study drug and who performed baseline and follow-up tests.

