### **5.5.1 Prohibited treatments during study period**

---

The following treatments are not permitted during the study:

- parenteral iron supplement (other than the initial study drug infusion)
- oral iron substitution

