### 6.3 Criteria for patient discontinuation

---

Patients may be discontinued from study treatment and assessments at any time. Specific reasons for discontinuing a patient for this study are:

- Voluntary discontinuation: participating patients are free to discontinue his/her participation in the study at any point in time, without prejudice to further treatment.
- Major protocol deviation
- Incorrect randomisation, i.e. the patient does not meet the required inclusion/exclusion criteria for the study
- Patient lost to follow-up
- Patient's non-compliance to study treatment and/or procedures

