### 10.1 Determination of sample size

---

This trial is designed to assess the effect of intravenous iron on peak oxygen consumption in heart transplant recipients with iron deficiency. We consider an increase in peak oxygen consumption of 1.5 ml/kg/min, equivalent to approximately half a Metabolic Equivalent of Task (MET), to represent a clinically meaningful improvement. An increase in O2 consumption of 1.5 ml/kg/min is approximately 6 % of the baseline maximal oxygen consumption in our heart transplant recipients. Data from the ACTION HF trial showed that a 6 % increase in peak oxygen consumption translated to an improved outcome in patients with heart failure. With a mean difference between the groups of 1.5 ml/kg/min and an expected repeat-measurement standard deviation of 2.5 ml/kg/min, a power of 80% and an  $\alpha$  of 5 %, we will need at least 44 patients in each group.

To allow for drop-out and to improve the chances of obtaining significance for secondary endpoints, we aim to include 100 patients.

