### **10.3 Population for Analysis**

---

The following populations will be considered for the analyses:

- Intention to treat (ITT) population: All randomised participants, regardless of protocol adherence.
- Per-protocol population (PP): Includes all subjects who have received study drug

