### **10.5 Statistical analysis**

---

All statistical tests will be performed using a two-sided 5 % level of significance. Continuous efficacy variables will be analysed using independent T-tests for comparisons between the treatment arms and baseline-adjusted ANCOVA for difference in changes. If necessary, values will be log-transformed to meet the assumptions of the tests. All analyses will primarily be analysed according to the intention-to-treat principle. Between-group differences in ordinal categorical variables, such as NYHA class, will be analysed using ordinal logistic regression, whereas the count variables will be assessed by Poisson regression. Demographic, efficacy and safety data will be summarised by treatment group using means, minimums, medians, maximums, interquartile ranges and standard deviations for continuous variables and frequency counts and percentages for categorical variables.

Per protocol analyses will be performed using the same methods as for the intention-to-treat analyses.

**The primary endpoint**, the baseline-adjusted between-group difference in peak oxygen consumption, will be calculated by ANCOVA according to the intention-to-treat principle, the statistical null-hypothesis being that the baseline-adjusted oxygen uptake does not differ between the two treatment arms. Secondary analyses will be made according to the per-protocol-principle.

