Forty-four patients in each group provides the trial with an 80 % power at an α of 5 % to show a difference between the groups of 1.5 ml/kg/min at an expected repeat-measurement standard deviation of 2.5 ml/kg/min. To allow for drop-out and to improve the chances of obtaining significance for secondary endpoints, we aim to include 100 patients.

7 General Considerations

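### The two per-protocol definitions differ, and neither excludes prohibited iron, ineligibility or an out-of-window test, so the analysis checks non-receipt of the infusion but not these deviations

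*SAP*

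**What the plan says.** Two definitions are in force. Protocol 10.3 has "Per-protocol population (PP): Includes all subjects who have received study drug". SAP 7.2.2 has "All subjects actually received the study drug and who performed baseline and follow-up tests". SAP section 12 describes its differences from the protocol as added detail and subgroup analyses; it does not mention this one.

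The comparator is the primary analysis. SAP 7.2.1 limits it, for the primary endpoint, to randomised patients with an adequate exercise test at both visits, whatever treatment they received. SAP 7.4 rules out imputation.

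The plan sets rules that a per-protocol set would normally draw on:
- Protocol 5.5.1, under "The following treatments are not permitted during the study", lists oral iron and any parenteral iron beyond the study infusion.
- Protocol 6.3 gives "Incorrect randomisation, i.e. the patient does not meet the required inclusion/exclusion criteria for the study" as a reason to discontinue a patient, alongside major deviation and non-compliance. Protocol 6.4.1 still seeks a final assessment where possible.
- SAP 5.1 places the infusion directly after randomisation and the efficacy tests at 6 months ± 2 weeks.
- SAP 8.3 keeps patients in the intention-to-treat analysis whether or not the infusion was completed, and sees no compliance issue.

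Per-protocol analyses are planned for the primary endpoint (protocol 10.5, SAP 9.2) and the secondary endpoints (protocol 10.5, SAP 9.2.1). The text after SAP 7.2.3 requires membership of every population to be settled before the blind is broken.

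**The concern.** A reader expects a per-protocol result to describe patients who followed the protocol. Here an infused and tested patient stays in the set after taking iron from elsewhere, after being found ineligible, or after a late test. If the per-protocol and primary results agree, that agreement could be taken to mean that deviations did not matter, although the set never removed them.

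Iron use outside the trial is the deviation most directly tied to the contrast. All participants are iron deficient, patients on oral iron may enrol if they agree to stop, and the placebo arm goes six months without iron. Non-study iron in that arm would pull both estimates towards zero by the same amount, and comparing the two analyses would not reveal it.

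**Working it through.** **1. The sets side by side, for the primary endpoint.**

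| Condition | Primary analysis, SAP 7.2.1 | Per-protocol, protocol 10.3 | Per-protocol, SAP 7.2.2 |
|---|---|---|---|
| Infusion received | not required | required | required |
| Infusion complete | not required (SAP 8.3) | not stated | not stated |
| Tests at both visits | required | not stated | required |
| Tests adequate | required | not stated | not stated |
| Eligible | not required | not stated | not stated |
| No prohibited iron | not required | not stated | not stated |
| Tested in window | not stated | not stated | not stated |

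On its wording, the SAP per-protocol set can differ from the primary set in two ways only: it drops patients who were not infused, and it could admit tests judged inadequate.

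**2. Deviators.** A deviator who is infused and tested adequately at both visits is in both sets. One who is discontinued and never retested is in neither. Neither case separates the two analyses.

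**3. Overlap.** The documents give no non-infusion rate. Assume 100 patients, all adequately tested, with u not infused. The overlap is (100 − u)/100, so u = 0, 1, 2 or 5 gives 100, 99, 98 or 95%.

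**4. The plan's own figure.** Inputs: "With a mean difference between the groups of 1.5 ml/kg/min" (protocol 10.1), "expected repeat-measurement standard deviation of 2.5 ml/kg/min" (SAP section 6), 80% power and "All statistical tests will be performed using a two-sided 5 % level of significance" (protocol 10.5).

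n per group = 2 (z₀.₉₇₅ + z₀.₈₀)² (SD/Δ)² = 2 × (1.960 + 0.842)² × (2.5/1.5)² = 2 × 7.85 × 2.778 = 43.6, rounded up to 44.

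The stated 44 reproduces, with 80.4% power. A t-based calculation gives 44.6, so 45 per group, with 79.5% power at 44. With 50 per arm and no dropout, SE = 2.5 × √(2/50) = 0.5 and power = Φ(1.5/0.5 − 1.96) = Φ(1.04) = 85.1%.

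**5. Size if deviators stay in.** Assume a share p of placebo patients takes iron and gains the full effect, with the SD unchanged and 50 analysed per arm. The expected difference is 1.5 × (1 − p), and power is Φ(difference/0.5 − 1.96). The last two columns remove the same share from each arm and assume that the remaining patients still show 1.5.

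| p | Expected difference, both analyses | Power, 50 per arm | Per arm after exclusion (rounded) | Power at 1.5 |
|---|---|---|---|---|
| 2% | 1.47 | 83.6% | 49 | 84.4% |
| 5% | 1.425 | 81.3% | 48 | 83.6% |
| 10% | 1.35 | 77.0% | 45 | 81.2% |
| 20% | 1.20 | 67.0% | 40 | 76.5% |

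Every p is assumed. Protocol 1.2 cites an oral-iron trial with no effect on oxygen uptake and presumes oral iron inadequate in these patients. For oral iron, full effect is therefore an upper bound on the dilution.

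**The case against.** The case for leaving the text alone has real weight.

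- **Role.** This is a superiority trial, and SAP 9.1 ties confirmation to the intention-to-treat ANCOVA alone. The per-protocol analysis is labelled secondary, and neither document calls it a robustness check. This stands and limits the stakes.
- **It does test something.** The primary analysis ignores receipt and the per-protocol set requires it. A reader might infer that the per-protocol analysis cannot test robustness at all; the documents do not support that.
- **Ineligible patients.** Protocol 6.3 allows them to be discontinued, so some will have no six-month test. It is too strong to say that all of them stay in. Those who are tested do.
- **Partial infusion and test adequacy.** The safety population uses the broader criterion of any study treatment, so receipt in 7.2.2 might mean the whole infusion. The adequacy condition might carry over, because per-protocol analyses use the same methods. Both points are ambiguous rather than clear errors.
- **Direction.** Iron use in the placebo arm pulls the estimate towards no difference, so it cannot create a false benefit.
- **Selection.** Iron use after randomisation is likelier in placebo patients who remain deficient. Excluding them removes a selected group mainly from one arm, and deciding blind does not cure that.
- **Other safeguards.** Protocol 5.5 has concomitant medication recorded, protocol 11.2 has significant deviations reported, and iron indices are measured during follow-up. These allow deviations to be described, but they do not define who leaves the set.

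What remains is that the definitions differ, and neither asks for adherence beyond being dosed and, in the SAP, tested.

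**Conclusion.** The point holds as a defect in a secondary analysis. The per-protocol set is defined in two ways and, under either, keeps dosed and tested patients with prohibited iron use, failed eligibility or an out-of-window test. Its result will probably be close to the primary result. That closeness is inferred from the single infusion given straight after randomisation, since no non-infusion rate is stated. Agreement between the two analyses would say little about these deviations.

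A reader might go further and conclude that the primary result is compromised. It is not: the intention-to-treat conclusion does not depend on this set. Nor should any row of the dilution table be read as an estimate. The range of 1.47-1.20 against 1.5 ml/kg/min rests on an assumed 2-20% of placebo patients taking iron with full effect.

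**What to change.** Put one definition in both SAP 7.2.2 and protocol 10.3: patients in the primary analysis (adequate tests at both visits) who
- received the complete assigned infusion,
- met the eligibility criteria,
- took no oral or parenteral iron other than the study infusion before the six-month test, and
- were tested within 6 months ± 2 weeks.

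Decide membership in a blinded deviation review, as the text after SAP 7.2.3 already requires. Protocol 10.4 allows changes to the statistical plan until database lock.

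Record non-study iron use from infusion through month 6. Protocol 5.5 is general, but the end-of-study medication item in 6.2.3 repeats the baseline wording and covers only 28 days around treatment start. As written, it could miss later iron use.

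The cost is wording, one recorded item and the blinded review. The set will be somewhat smaller, and excluding on iron use after randomisation may introduce selection bias. Report the number and reason for exclusions by arm, and keep the analysis supportive only.

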7.2.3 Safety Population

All subjects who received any study treatment (including control) but excluding subjects who drop out prior to receiving any treatment.

Each subject's inclusion or exclusion status regarding each analysis population must be determined prior to breaking the blind. The statuses must be documented in the final database prior to breaking the blind.

7.3 Covariates and Subgroups

The primary analyses (intention-to-treat population) will not be adjusted for baseline demographics. However, the primary endpoint and key secondary endpoints are calculated as the baseline-adjusted values (i.e. the follow-up result is adjusted for the baseline result of the same assessment in ANCOVA analyses) as specified for each endpoint.

We will perform binary subgroup analyses of the primary endpoint stratified by gender; age (median); whether the baseline transferrin saturation is $<$ or \geq 20 %; by whether or not the patient has anaemia (defined according to World Health Organization criteria of $<$ 12 g/l for women and $<$ 13 g/l for men); C-reactive protein (median) and whether or not iron parameters have normalised (to values no longer defined as iron deficiency as defined in "study objectives"). A forest plot will be used

to communicate the results. The subgroup analyses are exploratory only, as the trial is not powered to show differences across subgroups.

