### 7.1.6 Blood samples

---

We will draw blood samples for biobanking at baseline, prior to study drug infusion, and at 6 months. For biobanking, 18 ml blood should be drawn into tubes containing EDTA as the anticoagulant, 6 ml into tubes with citrate as the anticoagulant and 6 ml into tubes without additives. The tubes with EDTA and citrate should be put on ice immediately and be centrifuged at 3700 rotations/min for 20 minutes. The tubes without additives should be left at room temperature for 1-2 hours prior to centrifugation at 3500 rotations/min for 15 minutes. The tubes containing citrate as the anticoagulant should be put on ice immediately. The resulting plasma and serum, respectively, should be stored in multiple aliquots (at least four aliquots of serum and six aliquots of plasma per patient per visit), and labelled with the unique trial subject number, and the letter A signifying baseline, and the letter B signifying the end-of-treatment visit. The samples should be stored at -80 degrees Celsius until analysis.

Blood samples for safety will be collected at baseline, and 6 months after randomisation (end-of-study). These blood samples will be drawn and analysed at the study sites as per clinical routine. Troponin values will be used for endpoint analyses.

NT-proBNP will be assayed on a MODULAR platform (Roche Diagnostics, Basel, Switzerland). Plasma levels of CRP will be determined by a high-sensitivity particle-enhanced immunoturbidimetric assay (Tina-quant CRP [Latex] HS, Roche Diagnostic, Basel, Switzerland). TnT will be assessed using a high-sensitive immunoassay (Roche hs-TnT).

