5.3.1 Inclusion criteria

[figure not shown]
The following conditions must apply prior to administering the investigational medicinal product:

- Cardiac allograft.
- Presentation at least one year after heart transplantation.
- Iron deficiency defined as serum ferritin < 100 µg/l or ferritin between 100 and 300 µg/l in combination with a transferrin saturation < 20 %.
- Age between 18 and 80 years.
- Informed consent obtained and documented according to Good Clinical Practice (GCP), and national/regional regulations.

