9.2 Secondary Efficacy Analyses

Secondary, per protocol analysis will be performed for the primary endpoint. Exploratory subgroup analyses will be performed for the six subgroup categories mentioned in the section “Covariates and subgroups. The latter results will be communicated as a forest plot, and the interaction value of the covariates “treatment allocation” and the binary subgroup identifier in question will be reported at a significance level of 0.05.

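### Splitting age and C-reactive protein at the sample median for the exploratory interaction tests loses about a quarter to a third of the information on a roughly linear interaction

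*SAP*

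**What the plan says.** SAP 7.3 (Covariates and Subgroups) makes every subgroup analysis of the primary endpoint two-level. It begins "We will perform binary subgroup analyses of the primary endpoint stratified by gender; age (median") and later lists "C-reactive protein (median"). SAP 9.2 (Secondary Efficacy Analyses) uses the same groups for inference: the interaction between treatment allocation "and the binary subgroup identifier in question will be reported at a significance level of 0.05". The split therefore determines the reported test as well as the plot.

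Both variables are recorded on a continuous scale. The age criterion in SAP 5.3.1 is "Age between 18 and 80 years", and Table 1 of the SAP reports age in years. For CRP, Protocol 7.1.6 says: "Plasma levels of CRP will be determined by a high-sensitivity particle-enhanced immunoturbidimetric assay".

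SAP 7.3 also limits the weight of these analyses: "The subgroup analyses are exploratory only, as the trial is not powered to show differences across subgroups".

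**The concern.** A forest plot needs groups; an interaction test does not. Once age or CRP is cut at the median, a patient just above the cut counts the same as one at the far end of the range. The cut also depends on who happens to enrol, so another trial would split at a different value, and neither document gives a clinical reason for expecting the effect of iron to change there.

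What is at stake is a missed or poorly estimated effect modifier. CRP is a reasonable candidate on the trial's own rationale: Protocol 1.1 and 1.2 describe inflammation as raising hepcidin and disturbing iron handling, and describe recipients as having low-grade inflammation. A test that is already weak should not be weakened further without a reason.

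**Working it through.** **Inputs.** Target difference 1.5 ml/kg/min, SD 2.5 ml/kg/min, 44 per group, 80% power, alpha 5% (SAP 6; Protocol 10.1). Two-sided testing (Protocol 10.5). 1:1 allocation (Protocol 3). I assume that the plan's repeat-measurement SD of 2.5 serves as the ANCOVA residual SD. The sizes of interaction and the shapes of the age and CRP distributions are also assumptions, because the documents give neither.

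**1. The plan's own figure.** n per group = 2 × (1.96 + 0.8416)² × 2.5² / 1.5² = 43.6, so 44. It reproduces.

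**2. Information kept by a median split.** For a linear interaction, this is the squared correlation between the modifier and its two-level version.
- Normal modifier (or log-CRP, if CRP is log-normal): 2/π = 0.637, a loss of 36%.
- Moderately left-skewed age over 18 to 80: 0.667 by simulation, a loss of 33%.
- Uniform modifier: (√3/2)² = 0.75, a loss of 25%.

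For a normal modifier, a split analysis of 88 patients is worth a continuous analysis of 88 × 0.637 = 56. If CRP were log-normal and the interaction linear on the raw, unlogged scale, the loss would be 48% (log-SD 0.5) to 73% (log-SD 1.0).

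**3. Power, normal modifier, N = 88.** The standard error of the interaction per SD of the modifier is 2 × 2.5 / √88 = 0.533. Power is Φ(γ√R / 0.533 − 1.96), where γ is the interaction per SD, R = 1 for the continuous test and R = 0.637 for the split. A linear interaction of γ per SD makes the treatment effect differ between the median halves by γ × 2√(2/π) = 1.596γ.

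| γ (ml/kg/min per SD) | Difference between halves | Continuous: formula / simulation | Split: formula / simulation |
|---|---|---|---|
| 0.5 | 0.8 | 15% / 15% | 11% / 11% |
| 1.0 | 1.6 | 47% / 43% | 32% / 30% |
| 1.5 | 2.4 | 80% / 78% | 61% / 57% |

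The simulations use t-based tests, which is why most fall slightly below the normal formula; repeat runs agree within one or two percentage points. With no interaction, both tests reject about 5% of the time, so the gain in power does not come from extra false positives.

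**4. What the split test can detect.** At 80% power, the smallest detectable difference in treatment effect between the halves is 2.8016 × 4 × 2.5 / √88 = 3.0 ml/kg/min, twice the 1.5 for which the trial is sized.

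**5. The opposite case.** Suppose the effect steps by 2.0 ml/kg/min exactly at the median. The split has SE 4 × 2.5 / √88 = 1.066 and power Φ(2.0/1.066 − 1.96) = 47%. The continuous test has Φ(√0.637 × 2.0/1.066 − 1.96) = 32%. Simulation gives 45% and 30%. Here the split is the better test.

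**The case against.** The SAP already labels these analyses exploratory and unpowered, and its confirmatory claim rests on the primary ANCOVA alone (SAP 9.1). That stands, and it limits the point to an optional improvement.

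The split also has merits. It assumes no linear shape, is insensitive to extreme CRP values, gives a p-value for exactly the groups plotted, and is more powerful if the effect steps at the median. These stand too, so it would be wrong to say that the split has no benefit. But nothing in the documents suggests a step at the sample median, and taking logs deals with much of the skew in CRP.

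The gain is small where interactions are small: 15% against 11% at 0.5 per SD leaves both tests close to uninformative. The gap is widest for interactions that imply a difference between halves larger than the whole planned effect of 1.5. That is a fair limit on the practical value of the change.

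A reader might infer that a third of the trial's information is thrown away, or that the primary result is weakened. The documents do not support either. The loss concerns one type of contrast for two exploratory modifiers, and the primary model uses neither variable.

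A reader might also extend the criticism to transferrin saturation and anaemia. That does not follow. The 20% cut is part of the trial's own definition of iron deficiency (SAP 5.3.1), and anaemia is defined by sex-specific WHO criteria (SAP 7.3). Neither is a sample median, and pooled continuous haemoglobin would mix in sex, which is already a separate subgroup.

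**Conclusion.** The point holds as a cheap improvement. The SAP tests effect modification by age and CRP only through a median split with no stated clinical basis. If the interaction is roughly linear, that loses about a quarter to a third of the information on it: 25% for a uniform modifier, 36% for a normal one. At N = 88, the loss in power runs from about 4 percentage points at 0.5 ml/kg/min per SD to about 21 at 1.5.

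These figures rest on a linear interaction, a residual SD of 2.5 and, for the power figures, a normal modifier (CRP on the log scale). The direction reverses if the effect truly steps at the median. The primary estimate, its power and the safety analyses do not change.

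**What to change.** In SAP 7.3 and 9.2, state that for age and log-CRP the interaction estimate, confidence interval and p-value come from the ANCOVA of six-month peak oxygen consumption on baseline peak oxygen consumption, treatment, the continuous modifier and treatment × modifier. Report the estimate per decade of age and per doubling of CRP. Say that the CRP value is the baseline one (SAP 7.3 says so explicitly only for transferrin saturation), and how values below the assay limit are logged. Keep the median groups to draw the forest plot, with a footnote that those two p-values come from the continuous model. Leave transferrin saturation at 20% and anaemia by WHO criteria as defined cuts.

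The cost is a few sentences in the SAP, with no new data and no change of software. Protocol 10.4 allows changes to the plan until database lock, and fixing the form of the test before unblinding avoids a later choice between the two. The downsides are that linearity is assumed, the p-value no longer tests exactly the groups displayed, and power is lower if there is a real step at the median.

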### **6.2.2 3-month safety visit**

---

The study participants will be asked to visit their general practitioner for a clinical examination and blood sampling 3 months after study drug infusion. The blood samples will be sent to the laboratory at Oslo University Hospital, Rikshospitalet, for delayed (after end-of-study) assessment of haemoglobin, serum ferritin, serum iron, serum transferrin, and transferrin saturation.

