#### *Laboratory analyses*

Blood samples will be obtained to determine: Haemoglobin; white blood cell count, platelet count; serum potassium; serum sodium; glucose, glycosylated haemoglobin (HbA1c); creatinine; ALT; bilirubin; albumin; INR; CRP; N-terminal pro-B-type natriuretic peptide (NT-proBNP); total cholesterol; ferritin; transferrin, serum iron and total iron binding capacity. Blood for efficacy analyses must be drawn and appropriately labelled and stored for later analysis.

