## 7.2 Safety and tolerability

---

Safety will be monitored by the assessments described below as well as the collection of AEs at every visit. Significant findings that are present prior to the signing of informed consent must be included in the relevant medical history/ current medical condition page of the CRF. For details on AE collection and reporting, refer to Section 8.

For the assessment schedule, refer to Flow chart in Section 6.1.

Physical examinations will be performed at baseline and after 6 months. Vital signs including heart rate and blood pressure will be recorded before, during, and after study drug infusion. Monitoring must be especially vigilant with regard to signs of acute hypersensitivity reactions/abrupt hypotension.

Blood samples for safety analyses will be drawn at baseline and after 3 and 6 months. Local laboratory cut-points for normal values will be used for safety analyses. Haemoglobin; white blood cell count, platelet count; serum potassium; serum sodium; glucose, glycosylated haemoglobin (HbA1c); creatinine; ALT; bilirubin; albumin; INR; CRP; N-terminal pro-B-type natriuretic peptide (NT-proBNP); total cholesterol; ferritin; transferrin, serum iron and total iron binding capacity will be evaluated at each visit. In addition, blood samples for the measurement of iron stores will be drawn 3 months after study drug administration.

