4.2 Endpoints

The primary endpoint is the baseline-adjusted peak oxygen consumption as measured on a treadmill exercise test 6 months after study drug administration.

Secondary endpoints:

- The number of patients with absolute or functional iron deficiency
- Muscle strength as measured by a dynamometer hand-grip device
- Body composition
- Cognitive function as assessed by the Cambridge Neuropsychological Test Automated Battery
- Quality of life as assessed by the SF-36 and 5D EuroQoL questionnaires
- N-terminal pro-B-type natriuretic peptide (NT-proBNP)
- Cardiac troponin T (TnT)
- C-reactive protein (CRP)
- Inflammatory and vasoactive peptides.

5 Study Methods

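### The subgroup defined by normalised iron parameters is a post-randomisation response to the drug, so its two strata do not compare randomised groups

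*SAP*

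**What the plan says.** SAP 7.3 plans binary subgroup analyses of the primary endpoint by gender, age, baseline transferrin saturation, anaemia, CRP and "whether or not iron parameters have normalised (to values no longer defined as iron deficiency". Results go on a forest plot. SAP 9.2 applies one rule to all six: the interaction between treatment allocation "and the binary subgroup identifier in question will be reported at a significance level of 0.05". SAP 7.3 adds a caveat: "The subgroup analyses are exploratory only, as the trial is not powered to show differences across subgroups".

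Four other places bear on the sixth subgroup:

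- SAP 5.3.1 makes iron deficiency an entry condition ("Iron deficiency defined as serum ferritin" below the stated limits), and SAP 5.1 has the infusion given directly after randomisation.
- SAP 4.2 makes iron status a secondary endpoint: "The number of patients with absolute or functional iron deficiency".
- Iron status is measured twice after dosing. Protocol 6.2.2 sends the 3-month samples "for delayed (after end-of-study) assessment of haemoglobin, serum ferritin, serum iron, serum transferrin, and transferrin saturation", and Protocol 7.2 confirms that "blood samples for the measurement of iron stores will be drawn 3 months after study drug administration". The end-of-study laboratory list in Protocol 6.2.3 includes "ferritin; transferrin, serum iron and total iron binding capacity".
- SAP 7.3 does not say which of these visits defines normalisation.

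**The concern.** A subgroup analysis keeps the protection of randomisation only if the subgroup is fixed before treatment can affect it. Here nobody can be normalised at baseline, and Protocol 1.3.2 expects intravenous iron to replenish stores. The normalised stratum would compare iron patients who responded with placebo patients who left the iron-deficient range without the drug. The other stratum would compare iron patients who did not respond with placebo patients who stayed deficient.

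Any patient factor that affects both normalisation and exercise capacity then enters the treatment contrast. Protocol 1.2 says low-grade inflammation makes iron stores hard to interpret in these patients, so crossing the ferritin and transferrin saturation limits may depend on more than the drug.

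What is at stake is how one forest-plot row is read. It invites the conclusion that iron works, or fails, in patients who were repleted, and it cannot support either statement. The exploratory label does not help, because the reason given for it is power: a larger trial would give the same bias with a narrower interval.

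**Working it through.** **The plan's own figure.** Protocol 10.1 and SAP 6 use a difference of 1.5, SD 2.5, 80% power and two-sided 5%. n per arm = 2 × (1.960 + 0.842)² × 2.5² / 1.5² = 43.6, so 44, as stated. SD 2.5 and 44 per arm are carried forward.

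**Logic, without assumptions.** Everyone is deficient at entry; dosing follows randomisation; so normalised is a post-dose state. It is also the complement of a secondary endpoint, so the plan stratifies one outcome by another.

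**Illustration of size.** The documents give no normalisation rates and no link between normalisation and VO2, so both are assumed. Let Z be a standard normal tendency to normalise, with correlation r to the VO2 residual (SD 2.5). A patient is normalised if Z > c, with c set to give rate p1 (iron) or p0 (placebo); φ is the standard normal density.

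- Bias, normalised stratum = 2.5 r [φ(c1)/p1 − φ(c0)/p0]
- Bias, other stratum = 2.5 r [φ(c0)/(1−p0) − φ(c1)/(1−p1)]
- Interaction bias = the first minus the second

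For 90/20%: φ(c1) = 0.1755 and φ(c0) = 0.2800. At r = 0.2:

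- normalised: 0.5 × (0.195 − 1.400) = −0.60
- not normalised: 0.5 × (0.350 − 1.755) = −0.70

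| Iron/placebo normalised | r | Bias, normalised | Bias, not normalised | Interaction bias |
|---|---|---|---|---|
| 90/20% | 0.2 | −0.60 | −0.70 | +0.10 |
| 90/20% | 0.3 | −0.90 | −1.05 | +0.15 |
| 80/10% | 0.2 | −0.70 | −0.60 | −0.10 |
| 80/10% | 0.3 | −1.05 | −0.90 | −0.15 |
| 60/5% | 0.2 | −0.71 | −0.43 | −0.28 |
| 60/5% | 0.3 | −1.06 | −0.64 | −0.42 |

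Negative r reverses every sign; r = 0 gives zero throughout.

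**Precision.** At 90/20% the expected cells are iron 39.6 and 4.4, placebo 8.8 and 35.2.

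- SE, normalised: 2.5 × √(1/39.6 + 1/8.8) = 0.93
- SE, not normalised: 2.5 × √(1/4.4 + 1/35.2) = 1.26
- SE, interaction: 2.5 × √(sum of the four reciprocals) = 1.57. It is the same at 80/10% and 1.89 at 60/5%. An even baseline split gives 2.5 × √(4/22) = 1.07.

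The bias at 90/20% is thus about 0.6 to 1.0 of a stratum SE. The smallest cell expects about 4 patients (90/20% and 80/10%) or 2 (60/5%). It holds fewer than two with probability 5.7% (binomial, 44 at 0.10) or 34.7% (44 at 0.05).

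**Effect on reading.** With a true uniform effect of 1.5 at 90/20%, the two strata would show 0.60–0.90 and 0.45–0.80 for r = +0.2 to +0.3, or 2.10–2.40 and 2.20–2.55 for the same negative r.

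**Simulation with zero true effect** (6,000 runs per setting, same three pairs of rates, runs with a cell below two dropped). At least one stratum looked significant in 8.7–9.6% at r = 0, 14.8–17.7% at r = ±0.2 and 22.9–27.2% at r = ±0.3. The interaction test rejected in 4.5–5.8%.

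**The case against.** The case for leaving the row alone has real content.

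- The confirmatory claim rests on the primary ANCOVA (SAP 9.1), which this row does not touch. That stands.
- The one test SAP 9.2 specifies, the interaction, keeps close to its nominal level in the simulation. That stands: the damage is to the stratum estimates and to what the interaction is taken to mean.
- No within-stratum test is planned, and two looks alone give 1 − 0.95² = 9.75%. Only the excess over that belongs to this defect. Forest-plot intervals are nevertheless commonly read stratum by stratum.
- The correlation is assumed. At r = 0.1 the biases fall to 0.21–0.35 ml/kg/min, and the chance that a stratum looks significant (10–12%) barely exceeds its value at r = 0. The figures show a mechanism; they do not measure this trial's bias.
- Protocol 7.1 puts efficacy assessments at baseline and six months, and SAP 7.4 says efficacy data are collected twice, so six months is the natural reading of the missing visit. Granted; the visit still needs stating, but it is a clarification.
- Whether benefit tracks repletion is a fair question: Protocol 1.2 cites an oral-iron trial whose null result was put down to little change in iron stores. That argues for a separate, labelled analysis, not for a place among the baseline subgroups.

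These points limit the weight of the concern. None of them makes the strata randomised comparisons.

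**Conclusion.** The concern holds. The sixth subgroup is defined by a response to treatment, and SAP 7.3 and 9.2 present it as if it were a baseline characteristic. That conclusion follows from the documents and needs no assumption. The size does: across the three assumed pairs of rates and |r| of 0.2 to 0.3, stratum bias is 0.43 to 1.06 ml/kg/min, both strata in the same direction, with unknown sign and zero if r = 0. The harm is confined to one exploratory row, but the row would mislead as planned and is easily put right.

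A separate, minor point on which this does not depend: the haemoglobin figures disagree in unit. SAP 7.3 prints 12 and 13 g/l for anaemia; Protocol 4.4 and 5.3 and SAP 5.3.2 print 100 mg/l, which is 0.1 g/l; SAP Table 1 uses g/l. Coded literally, the SAP 7.3 limits would leave the anaemia stratum empty and its interaction not estimable.

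**What to change.** Before database lock:

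1. Delete the normalisation item from the subgroup list in SAP 7.3 and change six to five in SAP 9.2. State that the remaining five use baseline values; SAP 7.3 says so only for transferrin saturation.
2. Report iron status by arm as the secondary endpoint it already is, at a named visit.
3. If the relation between repletion and peak VO2 is wanted, give it its own section and figure, label it non-randomised and name the classifying visit.
4. Have the sponsor confirm the haemoglobin units and reconcile Protocol 4.4 and 5.3 and SAP 5.3.2 and 7.3 with Table 1.

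Items 1 to 3 cost SAP wording and one exploratory row. SAP 12 shows that the subgroups were introduced in the SAP, and Protocol 10.4 permits changes to the plan up to the day of lock. Item 4 also touches protocol wording. No data collection, alpha or sample size changes.
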